2. Poor compliance with eyelid scrubbing using tea tree oil (TTO)
3. Dead demodex mite on lash.
4. Contraindication of IPL: Skin Fitzpatrick scale V/VI, patients with pigmented lesions on the treatment area (Eyelid, Cheek).
5. Pregnancy or breastfeeding.
6. Active Skin disease: facial skin cancer, graft-versus-host disease, systemic lupus erythaematosus
7. Active eye infection: recurrent herpes simplex
8. Other lid disease ocular trauma, ocular deformity scar, exophthalmos, eyelid insufficiency
9. Patients with pigmented lesion on area of treatment.

We will use computer-generated random number allocation into 4 groups in a 1:1:1:1 ratio including seed number, with the outcome assessor blind and participant blind with allocation concealment:

- 1.) ShamLLLT + ShamIPL
- 2.) LLLT + ShamIPL
- 3.) IPL + ShamLLLT
- 4.) LLLT + IPL

***All groups receive mechanical with pharmacological treatment (Warm compression + Lid hygiene + 1% TTO) for 90 days with google form logbook for record compliance and prevent co-interventional treatments.

***All group with participant/investigator/interpreter blind.

Blinding and Allocation Concealment in Research Team:

1st Research Assistant : Allocates patients according to computer-generated random number allocation, ensuring allocation concealment, Evaluated VA , IOP , OSDI score by reads the questionnaire to the participant

2nd Research Assistant (The treatment administrator) : Administers IPL, LLLT, or sham treatments.

3rd Research Assistant : Conducts assessments using Keratograph and Lipiview2.

Main Researcher : Evaluates primary and secondary outcomes using case record forms, remaining blind to the treatment groups.

Intervention Description

Mechanical with pharmacological treatment : Warm compression 15 minutes + Lid hygiene + 1% TTO for 90 days

1%TTO : OCuSOFT Oust Demodex Eyelid Cleanser Foam Bottle 50ml (OCuSOFT, Richmond, TX) is the only commercially available medication in Thailand that contains 1% tea tree oil.

IPL : The Eye-light device (Espansione Marketing S.p.A., Bologna, Italy, waveleggths 1,200-1,500 nm, Delivery system 12cm²) (Thai FDA No 66-2-2-0012685) :

- Protective eye shields
- 5 flashes of light were applied for each eye (3 along the inferior orbital rim, 1 at the lateral canthus, and 1 applied horizontally along the inferior orbital rim)
- Therapeutic energy level (10–16 joules/ cm²) based on the degree of skin pigmentation.

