LLLT : The blue MY MASK-E (Espansione Marketing S.p.A., Bologna, Italy) (Thai FDA No 66-2-2-0012685)

- No eye shields
- Applying a special mask for 15 minutes, once a week for 4 weeks

ShamLLT : the MY MASK-E (Espansione Marketing S.p.A., Bologna, Italy) – No eye shields, applying a power off special mask for 15 minutes , once a week for 4 weeks

ShamIPL : the Eye-light device (Espansione Marketing S.p.A., Bologna, Italy) - Protective eye shields, 5 time for each eye with flashes of light off.

Epilation Strategies

the Modified Coston method as outlined by Gao et al. in 2005. In this method, two lashes containing cylindrical dandruff (CD) then additional **rotated around itself** were extracted from each eyelid of every participant using fine forceps. These lashes were then individually placed at opposite ends of a glass slide for observation under a slit-lamp biomicroscope (SL220; Carl Zeiss, Oberkochen, Germany) at a magnification of $\times 25$. This process resulted in four lashes of right eye being prepared across two slides for each participant. A coverslip was applied to each lash, followed by the slow pipetting of 20 μL of saline at the coverslip's edge until it surrounded the lash. Subsequently, 20 μL of 100% alcohol was pipetted at the same edge, extending the counting period for up to 20 minutes to facilitate the migration of embedded Demodex from the CD. The Demodex count was performed thrice under the microscope, and all samples were photographed using standard procedures by the same specialist. The presence of Demodex in at least one of the eight eyelashes was considered Demodex-positive

10. Data Collection:

Primary Outcome:

Mean of Demodex Count - the number of Demodex mites per eyelash on a total of 4 collarettes lashes epilation (2 from upper eyelid ,2 from lower eyelid and identification by anatomical imaginary line of nasal and temporal limbus) per right eye in 30 days after end of treatment. (8th week)

Secondary Outcomes:

1.Mean of Demodex Count - per right eye in 90 days after end of treatment.(16th week)

2.MGD staging (Severity)

[figure not shown]
OSDI questionnaire used to evaluate ocular dry eye symptoms.

OCULAR SURFACE DISEASE INDEX®					
Please answer the following questions by checking the box that best represents your answer.					
Have you experienced any of the following during the last week:					

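### The plan calls the outcome assessor blind, yet the assistant who allocates patients also reads them the OSDI, and no coded assignment is described that would reconcile the two

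*Combined protocol and SAP*

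**What the plan says.** All of the blinding text is in section 9 of the combined protocol and SAP (Research Methodology).

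- The randomisation sentence promises allocation "with the outcome assessor blind and participant blind with allocation concealment".
- A note after the four arms adds: "All group with participant/investigator/interpreter blind". The document does not define the interpreter.
- The role list describes the 1st Research Assistant thus: "Allocates patients according to computer-generated random number allocation, ensuring allocation concealment, Evaluated VA , IOP , OSDI score by reads the questionnaire" (the line goes on to say that it is read to the participant).
- The 2nd Research Assistant delivers the active or sham treatment.
- The 3rd Research Assistant "Conducts assessments using Keratograph and Lipiview2"; nothing is said about this person's blinding.
- The Main Researcher "Evaluates primary and secondary outcomes using case record forms, remaining blind to the treatment groups". This is the only team member individually described as blind.

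The OSDI appears among the secondary outcomes in section 10 and again in the Outcomes list in section 12. The form in section 10 is worded for self-completion: "Please answer the following questions by checking the box that best represents your answer". The visiting schedule has one data collection before treatment and two after it, at weeks 8 and 16.

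**The concern.** Allocation concealment and assessor blinding are different protections. Concealment keeps the next assignment unknown until the patient is entered. It does nothing afterwards to keep the allocator unaware of the arm. A person who allocates from the list is, unless the arms are coded, the team member least likely to be blind apart from the one giving the treatment. The plan puts that person between the participant and a subjective symptom score.

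If the reader knows the arm, the way questions are put, prompted and recorded can move answers towards the expected result. Section 6 states an expectation: the combination should do better than either light therapy alone, including on ocular surface parameters. At stake is whether a between-arm OSDI difference could be reported as assessor-blind.

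**Working it through.** The plan gives no figure on this point, so there is nothing to recalculate. The check sets the statements side by side.

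1. **Is the OSDI reader covered by the general blinding statement?** On its face, yes. The role line says this assistant evaluates the OSDI score, so the assistant is an outcome assessor, and section 9 says the outcome assessor is blind.

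2. **Is that compatible with the other task?** Only if the assistant can allocate without learning the arm, for example by passing on coded assignments whose key is held elsewhere. The document describes no coded labels, no key-holder and no route by which the assignment reaches the 2nd Research Assistant. Where masking of a measurement is planned, the plan can say so: section 10, item 7, has the meibography images masked before analysis. There is no equivalent for the OSDI.

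3. **Does the same assistant read the OSDI after treatment?** The role line gives no visit timing.
   - For baseline only: the line groups the OSDI with VA and IOP, and section 10, item 6, has BCVA and IOP recorded once at baseline.
   - For weeks 8 and 16: item 6 does not name the OSDI; an outcome used to compare treatments needs post-treatment values; these are the only post-treatment data-collection visits; and no other role is given the reading.
   - The second reading is the more likely one, but it is an inference. An OSDI read before allocation would not be affected.

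4. **Does the Main Researcher's blind evaluation repair this?** The plan does not set out the order of work or say that the Main Researcher obtains the answers. If that role works from answers already entered on the case record form, its blinding cannot undo an influence on how they were obtained.

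5. **Which outcomes are reached?** The Demodex count is not part of this assistant's tasks, so the primary outcome is untouched by this point. The severity table in Figure 1 contains an OSDI row, so MGD stage is reached only if that row is used to assign the stage.

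6. **Is this the only route to bias in the OSDI?** No. Sham LLLT means "applying a power off special mask for 15 minutes" without eye shields, and sham IPL is given "5 time for each eye with flashes of light off". Section 14 (Blinding Constraints) concedes that allocation is hard to hide from participants and investigators. For a patient-reported score that route may be the larger one. Section 14 does not mention the overlap of roles.

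**The case against.** The strongest reply is that the plan already says the outcome assessor is blind, that this assistant is an outcome assessor, and that a missing description of the mechanism calls for clarification and does not show a failure of blinding. The role line may also describe entry tasks only, since allocation, VA and IOP all belong there. The items and the response scale are fixed, which limits what a reader can do. The OSDI is one of many secondary measures and is not named in the analysis text of section 11. Reading a questionnaire aloud is a legitimate mode.

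Much of this stands. A reader might infer that the OSDI will be collected by someone who knows the arm. The document does not say that: both the knowledge of the arm and the reading at weeks 8 and 16 are inferred. A reader might also infer that the primary result is compromised, and nothing in the role list supports that.

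What does not stand is the view that only detail is missing. The general statement and the role list are both explicit, and following the role list as written opens the bias route unless an undescribed safeguard exists. Fixed items limit a reader's influence without removing it. The shams are meant to blind the person answering and do nothing to blind the person asking.

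**Conclusion.** The point holds as an internal conflict with an avoidable consequence: a declared blind assessor, and a role list that hands a subjective secondary outcome to the allocator, with nothing described that makes both true. It should be corrected, but it does not threaten the primary analysis.

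The size of any bias cannot be estimated. Neither a count of interviews nor the number of OSDI points per response category would be evidence of bias, so no magnitude is offered. The practical consequence rests on two assumptions: that the assistant sees the decoded arm, and that the same assistant reads the OSDI after treatment. If either is false, and the protocol says so, the point is resolved.

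**What to change.** Edit the role list in section 9 in one of two ways.

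- **Separate the tasks.** The allocator does not collect the OSDI. Choose one mode of administration and use it at every visit including baseline, so that the mode does not change between baseline and follow-up. It can be self-completion, as the form is worded, or reading by an existing team member whom the protocol states to be blind and without access to the list. The Main Researcher is a candidate because that role is already stated to be blind; the lack of access to the list should be written down as well. The 3rd Research Assistant would need both statements added.
- **Keep the tasks together.** If the allocator handles only coded assignments, state this and name the role that holds the key.

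In either case, say who collects the OSDI at baseline, week 8 and week 16, and define the interpreter or delete the term. If OSDI data have already been collected by an allocator who knew the arm, report the OSDI as not assessor-blind.

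The cost is a short edit and a small shift of work among existing staff, with no added visit or measurement. The document gives no workload figures, so spare capacity is assumed. The protocol does not say why reading aloud was chosen; if some participants need it, the option of a blind reader is the one to take. The change removes interviewer influence only and leaves the participant unblinding risk in section 14 where it is.

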A score of 100 corresponds to complete disability (a response of "all of the time" to all questions answered), while a score of 0 corresponds to no disability (a response of "none of the time" to all questions answered). Therefore, change from baseline of -12.5 corresponds to an improvement by at least one category in half of the questions answered.					
Subscale Scoring					
Subscales scores are computed similarly with only the questions from each subscale used to generate its own score. Therefore, any subscales analyzed separately would also have a maximum possible score of 100.					
The three subscales (vision-related function, ocular symptoms and environmental triggers) are broken out as follows:					
Subscale	Questions				
Vision-Related Function	4, 5, 6, 7, 8, 9				
Ocular Symptoms	1, 2, 3				
Environmental Triggers	10, 11, 12				

Meibum Quality.

Meibum Expressibility.

[figure not shown]
Telangiectasia grading: 0-3

3.Surface Staining: NEI Grading System.

4.Lipid Layer Thickness by LIPIVIEW

5.Noninvasive break-up time (NIBUT), tear meniscus height (TMH) , % Meibomian Gland Loss (MGL) by Keratograph 5M (OCULUS, Germany)

6.Corrected one times baseline , including BCVA, IOP.

7. After complete datacorrection : Meibography images will be masked and analyzed using an AI-assisted program to assess the following:

- Meibomian gland dysfunction staging (severity): MGD severity level and scored with 1-5 according to the 2011 MGD workshop (27) (Figure1)
- Meibomian gland area ratio: The proportion of the total visible meibomian gland area to the overall tarsal area in the eyelid
- Meibomian gland length: The linear measurement from the proximal to distal end of a meibomian gland, reflecting its elongation or shortening due to disease.
- Meibomian gland width: The horizontal width of individual meibomian glands, which helps assess gland atrophy or hypertrophy.

- Meibomian gland diameter deformation index: A metric for measuring irregularities in the shape and thickness of the glands, indicating glandular structural deformation.
- Meibomian gland tortuosity index: A measure of the curvature or twisting of the meibomian glands, used to assess changes in gland architecture.

Meibomian gland signal index: The intensity or brightness of the meibomian gland signal in meibography images, indicating gland density and activity

Visiting schedule:

1st visit	- Before treatment within 0-14 days (1 st Data correction+Epilation)

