For outcome ,Continuous data : Meibomian gland area ratio, Meibomian gland length and width,Meibomian gland diameter deformation index ,Meibomian gland tortuosity index, Meibomian gland signal index should be analyzed using ANOVA, while binary outcomes and ordinal data Meibomian gland dysfunction staging (severity) should be assessed using the chi-square test.

Any unavailable data will be treated as missing and will not be included in any calculations. The report will specify the percentage of missing data in each category. Statistical significance will be determined by a p-value < 0.05.

12.Ethical Consideration

The submission of the research proposal to the Institutional Review Board on Human Research at the Faculty of Medicine, Chulalongkorn University marks a pivotal step in ensuring the ethical oversight and approval of the prospective Randomized Control Trial (RCT)

Respect for Person:

Informed Consent: The principle of respect for persons underscores the importance of obtaining informed consent. Ensuring that participants have a clear understanding of the study's purpose, procedures, potential risks, and benefits is crucial.

Researchers employ transparent and comprehensive communication in the informed consent process, elucidating the randomization process, details of each intervention, and the freedom to withdraw at any point without repercussions.

Researchers will provide comprehensive information to ensure that volunteers understand the research well and make independent decisions regarding participation, without coercion or undue influence. If volunteers have legal representatives or proxies, they will be the ones reviewing the informed consent document and providing witness signatures. Researchers will seek permission from the hospital director at Chulalongkorn Hospital and will anonymize data using codes without disclosing patients' names, surnames, or hospital identification numbers.

Beneficence/Non-maleficence:

Risk-Benefit Assessment: Ethical research necessitates a careful evaluation of potential benefits against risks. Researchers must strive to maximize the positive outcomes of the study while minimizing any harm to participants.

Continuous monitoring of the interventions for unexpected risks and a commitment to modify or halt the trial if harms outweigh benefits are imperative to uphold the principles of beneficence and non-maleficence.

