Patients will benefit from receiving treatment for Demodex Blepharitis through eyelid scrubbing + 1% TTO (tea tree oil) and eyelid scrubbing + Low-Level Blue Light Therapy (LLLT) + Intense Pulsed Light (IPL) performed by specialized ophthalmologists. Volunteers will not receive any other benefits from participating in the research. All trial procedures will be tested by researchers and the team beforehand to identify potential issues. Safety will be paramount during the experiment, with basic first aid procedures in place and guidelines for referring participants in case of injuries or adverse effects

Justice:

Equitable Participant Selection: Justice demands fairness in participant selection, avoiding bias or discrimination. All eligible individuals should have an equal opportunity to participate, promoting inclusivity.

Researchers design the recruitment process to ensure diversity and representation across various demographics. The selection criteria based on scientific relevance, fostering inclusivity in the study population.

This research has clear inclusion and exclusion criteria, equally distributes risks and benefits, and employs a stratified study group allocation method.

Equitable Access to Benefits: The principle of justice extends to ensuring that the benefits resulting from the study are accessible to a broad population, preventing disparities in access to potential interventions.

Researchers proactively consider the implications of the study outcomes and work towards facilitating equal access to any effective interventions emerging from the trial, minimizing healthcare disparities.

Outcomes

Primary Outcome: Mean of Demodex Count - the number of Demodex mites per eyelash on a total of 4 collarettes lashes epilation per one eye in 30 days after end of treatment.

Secondary Outcomes:

- Mean of Demodex Count - the number of Demodex mites per eyelash on a total of 4 collarettes lashes epilation per one eye in 90 days after end of treatment.
- MGD Stage 1-5.

OSDI questionnaire used to evaluate ocular dry eye symptoms.

Meibum Quality.

Meibum Expressibility.

Telangiectasia grading: 0-3

- Surface Staining: NEI Grading System.
- LIPIMIEW used to measure Lipid Layer Thickness.
- The Keratograph 5M (OCULUS, Germany) used to measure noninvasive break-up time (NIBUT), tear meniscus height (TMH), % Meibomian Gland Loss (MGL)

13. Expected or Anticipated Benefit Gain

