- Patient Adherence: The effectiveness of interventions depends on patient adherence to treatment protocols. Challenges may arise if patients perceive the procedures as burdensome or experience difficulties maintaining compliance.

6. Limitations of AI Technology

- Algorithm Performance: AI-driven meibomian gland analysis is dependent on the quality of algorithms and training data. Variability in clinical conditions and diverse populations may impact the accuracy and effectiveness of AI models.

7. Integrating AI Insights into Clinical Practice

- Clinical Implementation: Translating AI-supported research findings into practical clinical guidelines and integrating them into routine practice requires extensive validation. Additional verification and refinement of study results may be necessary before AI-driven approaches can be widely adopted in clinical settings.

15. Risk and Investigator's Responsibility

1. Patient Privacy Protection:

Risk: The collection of sensitive health information necessitates the protection of patient privacy. Investigator's Responsibility: The investigator must adhere to data protection regulations, implement robust anonymization practices, and establish secure data storage and transmission procedures to safeguard patient privacy.

2. Participant Discomfort during Interventions:

Risk: Participants undergoing Photobiomodulation (LLLT) and Intense Pulsed Light (IPL) therapies may experience mild discomfort or temporary side effects.

Investigator's Responsibility: The investigator must thoroughly explain potential discomfort during the informed consent process and promptly address any participant concerns or adverse reactions.

3. Selective Reporting Bias:

Risk: There is a risk of selective reporting bias.

Investigator's Responsibility: The investigator must commit to transparently reporting all outcomes, fostering an unbiased and comprehensive understanding of the interventions' efficacy.

4. Bias and Accuracy in AI Analysis

Risk: AI models may have inherent biases or limitations that affect the accuracy of meibomian gland analysis, potentially leading to incorrect diagnoses or assessments.

Investigator's Responsibility: Researchers must rigorously monitor and evaluate the performance of AI systems, actively identifying and addressing biases or errors to ensure the reliability and credibility of study outcomes.

16. Timeline

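### The plan has no systematic adverse-event collection, and visual acuity and eye pressure appear to be taken only at baseline, so harm from the light treatments would show only indirectly or by spontaneous report

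*Combined protocol and SAP*

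**What the plan says.** All references are to the combined protocol and SAP.

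- **Acuity and pressure.** Section 10, Secondary Outcomes, item 6 reads "6.Corrected one times baseline , including BCVA, IOP". Section 9 (Blinding and Allocation Concealment in Research Team) gives the task to the first research assistant, "Evaluated VA , IOP , OSDI score by reads the questionnaire to the participant". It names no visit, and this assistant also allocates patients.
- **Outcomes.** The list in Section 10 and the repeated list at the end of Section 12 cover mite count, MGD stage, OSDI, meibum quality and expressibility, telangiectasia, staining, lipid layer and Keratograph measures. Section 10 adds AI meibography. Neither list contains an adverse event or a skin assessment.
- **Visits.** Data are collected before treatment and at weeks 8 and 16. Only treatment is listed for weeks 1–4. The logbook is for compliance and co-intervention.
- **Analysis.** Section 11 describes no safety analysis.
- **Monitoring.** Section 12, under Beneficence/Non-maleficence, states: "Continuous monitoring of the interventions for unexpected risks and a commitment to modify or halt the trial if harms outweigh benefits are imperative". It also mentions first aid and "guidelines for referring participants in case of injuries or adverse effects".
- **Expected harm.** Section 15, item 2 says participants "may experience mild discomfort or temporary side effects" and asks the investigator to "promptly address any participant concerns or adverse reactions".

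**The concern.** The ethics text describes weighing harms against benefits while the trial runs. The data plan supplies the benefit side in detail and gives the harm side no collection of its own. If the plan is followed as written, a transient eye reaction or a skin reaction after a session is recorded only if someone happens to report it, and nothing ensures that this happens equally in the four arms. A fall in acuity would have no post-treatment measurement to show it.

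This matters more because the protocol itself treats the intervention as little studied. Section 4.2 says that the effect of blue-light LLLT on the ocular surface in MGD has not been researched. The protocol also recognises a skin risk with IPL: it excludes the darkest skin types and pigmented lesions, and sets energy by pigmentation. Yet no skin assessment is scheduled. Section 15, item 3 commits the investigator to reporting all outcomes, but harm is not an outcome, so that safeguard does not reach it.

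**Working it through.** The plan states no safety figure, so there is none to reproduce. The check sets the passages side by side and then asks what complete collection could deliver at the planned size.

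**1. Reading item 6.** The visit schedule writes Data correction where data collection is plainly meant, and item 7 of the same list uses a similar form. Corrected in item 6 is therefore most naturally Collected, giving one measurement at baseline. Section 9 says who measures but not when, so it does not override this.

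**2. Change in acuity or pressure.** Change needs a baseline and a later value. Later values planned: 0 of 2 (weeks 8 and 16). No change can be calculated or compared between arms, whatever the sample size.

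**3. What other scheduled measures could show.**
- OSDI asks about light sensitivity, pain, and blurred or poor vision over the past week. At week 8 the window opens at about week 8 − 1 = 7, which is 7 − 4 = 3 weeks after the last session. At week 16 it opens at about week 15, 11 weeks after. A lasting symptom can appear; a short reaction in weeks 1–4 cannot.
- Staining and telangiectasia, if graded at weeks 8 and 16 with the other outcomes, can show persistent surface or lid-margin worsening.
- None of these records a skin reaction, measured acuity or eye pressure.

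**4. Group sizes.** Section 11 gives 18 × 1.2 = 21.6, rounded to 22 per arm; this is taken as stated. In the 2×2 layout, each modality is given in two arms (2 × 22 = 44) and any light in three (3 × 22 = 66).

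**5. Information from complete collection.** With zero events in n patients, the exact one-sided 95% upper bound is 1 − 0.05^(1/n). The chance of seeing at least one event at true rate p is 1 − (1 − p)^n. The documents give no rate, so a range of p is assumed.

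| Group | n | Bound at zero events | p = 1% | p = 2% | p = 5% | p = 10% |
|---|---|---|---|---|---|---|
| One arm | 22 | 12.7% | 19.8% | 35.9% | 67.6% | 90.2% |
| One modality | 44 | 6.6% | 35.7% | 58.9% | 89.5% | 99.0% |
| Any light | 66 | 4.4% | 48.5% | 73.6% | 96.6% | 99.9% |

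These figures hold only if every event is recorded. If only a fraction r is recorded, the bound applies to r × p, so the bound on p becomes bound ÷ r. With spontaneous reporting r is unknown and may differ between arms.

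**6. Formal comparison.** For 44 active against 44 sham (two-sided 5%, normal approximation, assumed rates), power is 35% for 2% versus 10% and 57% for 5% versus 20%. Safety results would be descriptive even with full collection.

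**The case against.** A reader might infer that the trial cannot detect harm at all, or that no safety data by arm would exist after the first session. The documents do not support that. OSDI, staining and telangiectasia are outcomes, data collection is scheduled at weeks 8 and 16, and worsening on them could be compared by arm. Sections 12 and 15 also provide for first aid, referral and prompt response. What stands is that these measures are planned for efficacy, miss the treatment weeks or the skin, and that the care provisions look after the individual without systematic recording.

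A reader might also infer a broken procedural promise. The monitoring sentence is a general statement of ethical principle; it sets out no procedure, reviewer or criterion. The gap is that nothing in the plan gives it effect.

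Nor should "No eye shields" for LLLT be taken as evidence of harm. It applies equally to the sham mask, and no passage links it to injury. Similarly, no passage connects either treatment with a change in pressure, so the case for repeating IOP is weaker than for acuity.

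The absence is of visible text only. Consent pages were removed, and the case record forms and referral guidelines are mentioned but not reproduced. That limits certainty, but the outcome, visit and analysis sections are all visible and contain no safety item.

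Finally, the zero-event bounds are not the size of this defect. They follow from the number of patients and would be the same with perfect collection.

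**Conclusion.** The point holds in limited form. The visible plan has no systematic harm collection behind its monitoring statement, and it cannot measure change in acuity or pressure. In size: BCVA and IOP at 0 of 2 post-treatment assessments, adverse events in neither outcome list, and no assessment listed for the 4 treatment sessions. Some lasting symptomatic or surface harm could still emerge indirectly. Skin reactions and short-lived reactions in weeks 1–4 could reach the record only by spontaneous report.

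This rests on reading Corrected as Collected, and on the unseen forms and consent text containing no adverse-event schedule. It does not affect the primary mite-count analysis. It should be corrected because the change is small and the missing information cannot be recovered afterwards.

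**What to change.** 1. Add a short adverse-event form, covering eye and skin, to every treatment and follow-up visit. State the definition and grading used, and name who reviews the forms as they accumulate.
2. Repeat BCVA, and IOP with it, at the existing week-8 and week-16 visits. Give this to a masked team member who neither allocates nor treats, for example the assistant who runs the Keratograph and Lipiview assessments, and confirm that person's masking in Section 9. The assistant who allocates patients should not do it.
3. Reword item 6 so that the timing is unambiguous.
4. In Section 11, plan to report events and change in BCVA and IOP by arm and pooled by factor (about 44 patients per modality, 66 given any light), with exact confidence intervals for event rates. Describe the results as descriptive.

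The cost is a few minutes per visit, one form and some added work for the masked assessor, with no extra visits or equipment. The limitation that remains is precision: the intervals will be wide, and the report should say so.
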